The study will end for subjects when they have completed the second follow-up visit scheduled 25 (\pm 4) days after the final day 7 visit, or at the time they chose to withdraw from the study or are removed from the study by decision of the principle investigator.

VI. Subject Selection

VI.a. Inclusion Criteria

Subjects

1. Age \geq 18 years and have had clinical type 1 diabetes for at least one year
2. Diabetes managed using an insulin pump for \geq 3 months
3. Prescription medication regimen stable for $>$ 1 month (except for medications that will not affect the safety of the participant and are not expected to affect any outcome of the study, in the judgement of the principal investigator)
4. Willing to wear one Dexcom CGM sensor, and up to two steel cannula infusion sets (6 mm Contact Detach) and change infusion sets frequently (if the subject is known not to tolerate steel infusion sets then a plastic set may be used)
5. Have used a CGM for at least one cumulative month over the last 24 months
6. Willing to stay within a 250-mile radius of the designated base throughout the study. Air travel is not permitted.
7. Informed consent obtained before any trial-related activities
8. Have a designated contact (an adult \geq 18 years of age) willing to serve as an emergency contact for them throughout the study.

Designated Contacts

1. Age \geq 18 years
2. Have an established relationship with the study participant
3. Willing to answer questionnaires about their experience with the participant's diabetes and the bionic pancreas
4. Willing to answer calls and check on the participant's wellbeing as needed
5. Able to provide informed consent (e.g. no condition that impairs cognition or judgement)

VI.b. Exclusion Criteria

1. Unable to provide informed consent (e.g. impaired cognition or judgment)
2. Unable to safely comply with study procedures and reporting requirements (e.g. impairment of vision or dexterity that prevents safe operation of the iLet, impaired memory, unable to speak and read English)
3. Current participation in another clinical trial with administration of investigational drug.
4. Current participation in another diabetes-related clinical trial that, in the judgment of the principal investigator, will compromise the results of this study or the safety of the participant
5. Previous exposure to dasiglucagon (otherwise known as ZP4207)

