Volunteers who fit the selection criteria will be considered as candidates for this study. We will contact individuals who have previously inquired about participation in our studies and have asked us to have their contact information kept on file. In addition, advertisements for the study may be posted at the MGH Diabetes Center and other places, and may be distributed in the weekly broadcast email of research studies seeking volunteers. A letter may be sent to adult endocrinologists in the Boston metropolitan area as well as selected nearby endocrinologists informing them of the study and asking them to refer to any eligible patients who might be interested. We will post information about the trial along with contact information on our website www.bionicpancreas.org and on www.clinicaltrials.gov.

No individuals will be excluded based on gender or race. An equal gender distribution between males and females is anticipated.

V. Subject Enrollment

V. a. Number of Subjects

It is expected that we will have 10 subjects complete the study with a consistent protocol. We expect that the experiments and the analysis can be accomplished over a period of 6-12 months. Up to 20 subjects will be enrolled. The upper bound is based on the expectation that some volunteers will be excluded after the screening visit and the possibility that some experiments may have to be discontinued before completion (due to, for instance, intercurrent illness or subject withdrawal). Each subject will have up to

two designated contacts enrolled who will serve as an emergency contact for the participant, and complete questionnaires based on their experience with the bionic pancreas. Therefore, total enrollment for the study including these partners will be 60.

V. b. Enrollment and Consent Procedures

Prospective participants will be briefed by a study staff member by phone or by e-mail regarding the study procedure and the inclusion and exclusion criteria. Potential subjects will be sent an informed consent document by mail, fax or e-mail.

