- A urine pregnancy test will be performed in pre-menopausal female volunteers. If the test is positive the volunteer will be informed of the result and the visit will be ended.
- Height, weight, heart rate and blood pressure will be measured. An EKG will be performed.
- If the volunteer is not excluded based on historical criteria, blood pressure, EKG or urine pregnancy test, blood will be drawn for hemoglobin A1c, and fractionated metanephrines if applicable. A study MD or NP will review the case report form to determine subject eligibility. If subjects are not eligible to continue in the study the results of abnormal tests will be reported to the subjects and to a health care provider of their choosing.
- A questionnaire will be administered to assess impaired awareness of hypoglycemia.
- Subjects who have been screened and are eligible can participate without having to be re-screened for a period of 3 months. The study staff should verbally confirm that there have been no health events that would make them ineligible at every study visit, and rescreen subjects for eligibility if it has been greater than three months.
- Once enrolled, subjects will identify up to 2 designated contacts (caregivers/family

members/friends) who are willing to serve as an emergency contact for the participant, requiring them to answer phone calls and check on the participants wellbeing as needed. If possible, they would also be an appropriate person to answer questionnaires about their experiences and attitudes towards the subject's diabetes and the impact of the bionic pancreas.

- Study staff will confirm the designated contacts are able to provide informed consent and are willing and able to serve as an emergency contact, and can recognize and treat hypoglycemia. If possible, they will confirm the contacts also have an appropriate relationship with the study participants to answer these questionnaires. Informed consent will be obtained from these contacts, and study staff will collect basic demographic information (age, sex, race/ethnicity) as well as contact information.
- All designated contacts will be trained in the symptoms of hypoglycemia and response to severe hypoglycemia, including the administration of glucagon. They will also be trained to recognize the symptoms of hyperglycemia, and when to contact study staff and local EMS.

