- Designated contacts will complete two validated questionnaires, the Diabetes Distress Scale and the INSPIRE AID, which are both designed to be completed by partners. These questionnaires will be completed at baseline, and at the end of each study arm.
 - They will have the option to complete these forms in person at a study visit, or online using RedCap.

VI. d. ii. Randomization of Visit Order

Once the subject has been enrolled and eligibility has been established, subjects will be randomized to one of two possible visit schedules.

VI. d. iii. General Policies and Protocols for Days 1-7 of Both Study Arms

- Subjects will remain within a geographic boundary established based on 250 miles from the designated base for study personnel at all times and will avoid any air travel.
- Subjects will keep a charged mobile phone on their person (or at their bedside) at all times and will answer calls from the study staff.
- Study subjects will keep a Contour Next One glucometer easily accessible at all times in case a calibration is needed, and they will do all calibrations with this meter. They will keep a glucometer, fast-acting carbohydrates, and a glucagon emergency kit easily accessible at home for hypoglycemia as needed.
- Subjects should use the study provided Contour Next One glucometer for all BG checks throughout the study. They are encouraged to check their BG at least four times a day, before meals and before bedtime. They will also be encouraged to check before exercise and at intervals during exercise, and for any symptoms of hypoglycemia. There are no restrictions on additional checks and subjects should check as often as they wish to confirm the accuracy of the Dexcom CGM and for safety.
- Subjects will wear the study provided 6 mm steel cannula (Contact Detach) infusion sets throughout the study. If the subject is known not to tolerate steel infusion sets or are found not to do well with them during the study, then an alternative infusion set may be used.
- Subjects will not use any recreational drugs or drugs of abuse, other than alcohol. The need to take prescription drugs that dull the sensorium, reduce sensitivity to symptoms of hypoglycemia, or hinder appropriate decision-making may be grounds for exclusion from the trial or discontinuation of participation, a decision that will be made by the principal investigator.

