The primary endpoint evaluates if the iLet system performs as designed, receiving CGM signals and delivering drug doses (insulin and, when applicable, glucagon) calculated by the control algorithm with an acceptable degree of reliability and accuracy. No formal test of the primary endpoint is planned.

The null hypothesis tested for the key secondary endpoint is:

The amount of hypoglycemia using the bihormonal configuration of the iLet is equal to the amount of hypoglycemia using the insulin-only configuration of the iLet.

The proportion of time with CGM glucose < 54 mg/dl across days 2-7 estimates the amount of hypoglycemia.

VII.b Sample Size Determination

No formal statistical comparisons have been done for this study. This study is primarily intended to verify that the iLet is operating as expected (based on its design and on bench testing) in each configuration in the outpatient setting. A sample size of 10 subjects in a crossover design is considered adequate for this purpose.

VII.c Populations for Analyses

Adult subjects (≥ 18 years old) with type 1 diabetes.

VII.d Statistical Analyses

VII.d.i General Approach

An intention-to-treat analysis will be performed. Descriptive statistics will be used to summarize patient characteristics and assessments. No formal testing will be conducted to establish superiority. In general, all data will be summarized with descriptive statistics for each treatment group. Unless otherwise specified, continuous data will be summarized by presenting the number of non-missing observations, mean, standard deviation (SD), median, minimum, and maximum. Categorical data will be summarized by presenting the number of patients and percentage for each category. P-values can be displayed to aid interpretation, not for inference. Tables, figures and listings of all primary, secondary and safety endpoints will be created.

Baseline and demographic data will be summarized using descriptive statistics. All comparisons will be between treatments within patients. Listings of individual patient data will be presented.

Data from periods when the bionic pancreas was not in use will be included, if available (Dexcom CGM data may not be available in some failure modes). In cases where an arm was not completed we will use the available data from that arm in the data analysis.

VII.d.ii Analysis of the Primary Efficacy Endpoint

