The primary endpoint is whether the iLet operates as designed during the study arms. An arm will be considered to have successfully met its primary endpoint if each of the following is true during the time that the iLet is powered on over the entire treatment period (days 1–7):

1. The percentage of time that valid CGM glucose readings are captured by the iLet is $\geq 80\%$. Sensor warm-up periods, occasions of failed communication between the iLet and sensor–transmitter unit, or other sensor failure conditions are all counted as times when valid CGM glucose reading are not captured.
2. The percentage of the time that each drug channel (insulin, and if applicable, glucagon) is available is $\geq 95\%$. A channel is considered to be available if a cartridge is successfully loaded, there is no pending occlusion alarm or other system failure to prevent attempting a delivery on that channel, and the cartridge is not yet considered empty.
3. The ratio of cumulative drug doses delivered to cumulative drug doses attempted is between 0.95 and 1.05, inclusive, for insulin and, if applicable, for glucagon. Attempted doses refer to calculated doses that are issued for delivery when the channel is available. Doses delivered refers to the dose amounts reported back by the motor controller after the delivery attempts are completed.

If all three evaluations hold true for a patient’s treatment period, the patient-period is operationally successful. The proportion of patients that are operationally successful will be presented by pump type.

VII.d.iii Analysis of the Secondary Endpoints

The proportion of time spent with CGMG < 54 mg/dl and the mean CGMG are analyzed using methods for paired data. The treatment means and mean difference between treatments will be estimated together with the corresponding 95% confidence interval and compared using a paired t-test for normally distributed data or Wilcoxon signed-rank test for non-normally distributed data. Time < 54 mg/dl and mean glucose will be computed from all available CGM data during days 2-7 for both study arms.

All questionnaire data for patients who have completed a minimum of 4 days with a device will be included. Patients who do not complete a questionnaire will be excluded from the patient analyses. Results will be compared by Wilcoxon signed-rank test.

VII.d.iv Safety Analyses

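### Does the signed-rank comparison of designated-contact questionnaires need a stated unit of analysis, given up to two contacts per participant?

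*Combined protocol and SAP*

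**What the plan says.** Quality of life and treatment satisfaction are secondary endpoints in section II, for participants and also for their caregivers, partners and family. The contacts supply the second part.

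- **Number of contacts.** Inclusion criterion 8 (Subject Selection, VI.a) requires one: "Have a designated contact". At screening (VI.d.i) "subjects will identify up to 2 designated contacts". Section V.a also allows two per participant and expects them to "complete questionnaires based on their experience with the bionic pancreas".
- **Instruments.** VI.d.i: "Designated contacts will complete two validated questionnaires, the Diabetes Distress Scale and the INSPIRE AID". They are answered at baseline and after each arm, so each contact can give one between-arm difference.
- **Analysis.** VII.d.iii includes questionnaire data for patients with at least 4 days on a device. It adds "Patients who do not complete a questionnaire will be excluded from the patient analyses" and then "Results will be compared by Wilcoxon signed-rank test". Contacts are not named there, and VII.c defines the analysis population as adults with type 1 diabetes.
- **General rules.** VII.d.i states "All comparisons will be between treatments within patients" and "P-values can be displayed to aid interpretation, not for inference". It also rules out formal superiority testing and keeps the available data from an arm that was not completed.

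**The concern.** The signed-rank test treats the paired differences as independent of one another. Two contacts of the same participant are reacting to the same person's two weeks on the two configurations, and treatment order is randomised by participant, not by contact. Their between-arm differences are therefore likely to be positively correlated. An analyst with a file of contact records could compare each contact with him- or herself and believe the plan had been followed. Any p-value for partner distress or satisfaction would then tend to be too small, because the number of independent pairs would be overstated.

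**Working it through.** **Enrolment figure.** V.a gives a total of 60. This is 20 participants + 20 × 2 contacts = 60, so two contacts per participant is the planned ceiling.

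**Inputs.** The 10 expected completers come from V.a. One or two contacts each comes from VI.a, VI.d.i and V.a. The documents do not give the number k of participants with two answering contacts, the correlation ρ of the two contacts' between-arm differences, or a significance level for questionnaires. These are assumptions: k = 2, 5 or 10; ρ from 0 to 0.5, with 0.3 to 0.5 as the main range; two-sided 5%.

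**Effective number of pairs.** With contact-level entry there are 10 + k pairs. The variance of their mean is inflated by

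1 + (Σm² / Σm − 1)ρ = 1 + [2k / (10 + k)]ρ,

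where m is the number of contacts per participant. For ρ = 0.3 and 0.5:

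- k = 10: inflation 1.30 and 1.50; 20 / 1.30 = 15.4 and 20 / 1.50 = 13.3 effective pairs
- k = 5: inflation 1.20 and 1.33; 15 / 1.20 = 12.5 and 15 / 1.33 = about 11.2
- k = 2: inflation 1.10 and 1.17; 12 / 1.10 = 10.9 and 12 / 1.17 = 10.3

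**False-positive rate.** This was simulated with no true effect, normal differences without ties, the exact signed-rank test and 200,000 runs per setting. Two separate simulations covered k = 5 and k = 10. Where they differ, it is by about 0.1 percentage point, and both values are shown.

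| Participants with two contacts | Pairs | ρ = 0 | ρ = 0.2 | ρ = 0.3 | ρ = 0.5 |
|---|---|---|---|---|---|
| 2 of 10 | 12 | 4.2% (exact level) | not run | 5.2% | 5.9% |
| 5 of 10 | 15 | 4.8% | 6.2% | 6.9–7.0% | 8.4–8.5% |
| 10 of 10 | 20 | 4.7–4.8% | 7.0% | 8.1–8.2% | 10.6% |

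At the extreme of ρ = 0.9 the rate is 12.2% for k = 5 and 15.6% for k = 10. With one value per participant it stays at 4.8 to 5.0% in every setting run. Questionnaire scores are discrete and will have ties, so the decimals should not be read closely.

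**Does the plan lead there?** The inflation needs three things: the test is applied to contacts, both contacts of a participant answer, and each is entered as a separate pair. On the first, VII.d.iii speaks only of patients and VII.c does not include contacts. A purely descriptive summary of contact data, which VII.d.i provides for data in general, is an equally open reading. On the second, only one contact is required, and VI.d.i asks only that contacts be suited to the questionnaires where possible. On the third, the rule of comparing treatments within patients leans the other way.

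**The case for a change.** The strongest case for a change is that the gap is real and cheap to close. The rule on within-patient comparisons does not settle it, because a contact is not a patient and the rule does not say how two scores become one. Displayed p-values are meant to help interpretation, and one based on miscounted pairs would mislead in that role. Weighting is affected even without a p-value: if 5 of 10 participants have two contacts, that half supplies 10 of 15 records (67%) in a contact-level summary. Section III.a says questionnaire information, including that from partners, will inform how the final device is configured.

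Part of this stands. The plan is silent on combining two contacts, and contact-level entry would be the wrong way to run a paired test. The rest carries less weight. A mean over responding contacts is a legitimate description of contacts. It departs from the participant-level mean only if responses differ by number of contacts, and nothing in the documents suggests that they do. Section III.a ties no configuration choice to a p-value or to contact results alone. Restricting all contact data to those who answered after both arms would also have a cost, since it would drop one-arm data from the descriptive summaries, whereas VII.d.i keeps available data.

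**Conclusion.** No change to the plan is needed. The unit for contact questionnaires is an unstated detail, and the harm arises only if an analyst fills it badly, against the lean of the plan's own general rule. A sensible analyst making a paired comparison would use one value per participant and arm, either the mean over that participant's contacts or one contact fixed in advance. All available contact data would stay in the summaries, with a note of how many participants had one contact and how many had two.

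If both contacts were entered separately, a nominal 5% would become about 5 to 6% with two two-contact participants and about 8 to 11% with all 10. These figures rest on an assumed correlation of 0.3 to 0.5, which the documents do not give, and there is no inflation at zero correlation or with one answering contact each. The p-values concerned are descriptive, for one group of respondents within two secondary endpoints. The primary endpoint, the glucose endpoints and the participants' own questionnaires are untouched, and no trial conclusion would change.
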